STATISTICAL ANALYSIS PLAN FOR
“Seasonal Differences in Home Dialysis Uptake and Initiating Dialysis in the Hospital”

PROTOCOL ID: HS-18-00530-2

SECONDARY ID: K08DK118213

Version #1

Last Modified: 6/8/2021

PI: [name], MS

Keck School of Medicine of the University of Southern California

Cohort construction

- 1) Identify incident adults who started dialysis from 12/1/2007 – 11/30/2017
 - a. USA, no transplant or death in first 90 days, dialysis first modality
 - b. Has medical evidence form
 - c. Has Medicare AB 30 days prior to first date of dialysis
- 2) Create season/year variables based on the first date of dialysis
 - a. Season is winter, spring, summer, fall
 - b. For December, use the following year (i.e., we want 12/2012-2/2013 to be “winter of 2013”)
- 3) Outcomes:
 - a. Type of dialysis at start (home versus in-center), end of month 3, 6, 9, 12
 - i. Indicator for whether patient is alive by end of month 3, 6, 9, 12
 - b. Time until home dialysis
 - i. Indicator for whether patient used home dialysis
 - ii. Censor for transplant, death, day 360, or end of follow-up, whichever occurs soonest
 - c. Whether the patient had a hospitalization in the 14 days prior to first_se (include if first_se occurs during the hospitalization)
 - i. Categorize the hospitalization as acute infectious respiratory OR one of the following cardiac (myocardial infarction, stroke/TIA, arrhythmia, fluid overload) if either of the following is true:
 1. Any of the diagnosis codes has one of the following CCS: 1, 2, 3, 7, 97, 100, 108, 109, 112, 122, 123, 125, 131
 2. The principal diagnosis code is one of the following CCS: 101, 105, 106, 107, 129
 3. (We use CCS categories as constructed by AHRQ)
 - ii. Otherwise, the hospitalization is non-acute cardiac/infectious-respiratory
- 4) Covariates
 - a. Patient level
 - i. Age
 - ii. Sex
 - iii. Race
 - iv. Ethnicity
 - v. Whether patient is dual eligible
 - vi. Employment status
 - vii. Type of dialysis access at the start of dialysis
 - viii. Whether patient had a nephrologist prior to dialysis start
 - ix. Primary reason for ESRD
 - x. Comorbidities using the CMS 2728 Form
 - b. Facility characteristics
 - i. Profit status
 - ii. Chain vs. independent
 - iii. Size of facility (Number of patients)
 - iv. Staff : patient ratio
 - v. ESRD Network
 - c. Zipcode Characteristics

- i. Median income
 - ii. High school graduation rate
 - iii. % below poverty

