 - d. Yearly level fixed effects (an indicator for each year as defined above)
- 5) Using multiple imputation (chained equations and ordinal logit) to impute missing characteristics. We use ordinal logit because all variables (including continuous ones) will be modeled as categorical variables.
 - a. Variables used for imputation: Covariates as above, type of dialysis at start, whether the patient had an acute cardiac/infectious-respiratory, or other hospitalization within 14 days of dialysis
 - b. 10 imputations
 - c. Recombine estimates using Rubin's rules

PLANNED ANALYSES

Table 1: Descriptive statistics (frequencies and percentages) of all covariates, stratified by season of dialysis start

Table 2: Descriptive statistics (frequencies and percentages) of each hospitalization type by season of year. Compute the ratio in frequency between winter and summer

Figure 1: Unadjusted seasonal differences in home dialysis and # of patients starting with a hospitalization

- A) Y axis: # of in-center patients, X axis: time; series: show patients who start with a hospitalization and patients who start without a hospitalization
- B) Y axis: # of home patients, X axis: time; series: show patients who start with a hospitalization and patients who start without a hospitalization
- C) Compute log rank test (p-value)

Figure 2: Differences in time to home dialysis uptake by season and by whether patients start with a hospitalization

- Kaplan-Meier curves, censoring for death, transplant, loss to follow-up (1 year maximum follow-up)
- A) By season of year
- B) By whether patients start with and without a hospitalization
- C) Compute log rank test (p-value) for A & B

Figure 3: Mortality by season of year

- Kaplan-Meier survival curves, censoring for loss to follow-up
- By season of year
- Compute log rank test (p-value)

Regressions (using multiple imputation). Robust standard errors for all models.

- A) Logits (each outcome is a different regression)
 - a. Outcome: home dialysis at start, months 3, 6, 9, 12
 - b. Exposure: season of year, whether hospitalized (and type of hospitalization)

- c. Covariates: as above
- B) Cox
 - a. Outcome: time to home dialysis (st set data)
 - b. Exposure: season of year, whether hospitalized (and type of hospitalization)
 - c. Covariates: as above
- C) Subgroup analyses
 - a. Repeat A and B but interact the exposures
 - b. For each of the subgroups, compute the following:
 - i. winter + winter##hospitalized

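### Figure 2 censors death and transplant in Kaplan-Meier curves of home dialysis uptake, which slightly overstates uptake; the entry of patients already at home at start also needs a written rule

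*SAP*

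**What the plan says.** Figure 2 (SAP, Planned Analyses) is titled "Differences in time to home dialysis uptake by season and by whether patients start with a hospitalization". Its method is "Kaplan-Meier curves, censoring for death, transplant, loss to follow-up (1 year maximum follow-up"), with panel A by season, panel B by hospitalized start, and log-rank tests for both. The matching outcome, Cohort construction 3) b, uses the same censoring: "Censor for transplant, death, day 360, or end of follow-up, whichever occurs soonest". Its event is "Indicator for whether patient used home dialysis", with no restriction to patients who start in-center.

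Outcome 3) a records "Type of dialysis at start (home versus in-center), end of month 3, 6, 9, 12", and home dialysis at start is one of the logit outcomes in Regressions A. The cohort therefore includes patients who are at home on the first day. Regressions B models time to home dialysis and gives no time origin and no entry rule for these patients.

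Three further items bear on the point. The cohort requires "no transplant or death in first 90 days, dialysis first modality". Figure 3 compares mortality by season. The only planned sensitivity analysis is complete case.

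**The concern.** Kaplan-Meier treats a censored patient as someone who could still have the event later. That is reasonable for loss to follow-up. It is not reasonable for a patient who has died, or in the ordinary case for one who has been transplanted. One minus Kaplan-Meier then estimates uptake in a hypothetical population without death or transplant, and this exceeds the share of actual patients who take up home dialysis. The excess grows with the competing hazard, so two groups with the same switching hazard but different mortality would show identical curves while their actual uptake differs.

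The second issue is a data step. Measured from the first date of dialysis, which is the evident origin, a patient at home at start has zero time. If the survival set-up drops such records, Cox B and Figure 2 describe switching after an in-center start and not the any-use outcome that 3) b defines.

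**Working it through.** The SAP states no event rate, sample size or power, so there is no planned figure to reproduce. All rates below are assumptions.

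**Size of the excess in Figure 2.** Inputs from the SAP are follow-up to day 360 (outcome 3) b) and no death or transplant before day 90 (cohort rule). Hence T = 360/365.25 = 0.9856 yr, t = 90/365.25 = 0.2464 yr and T − t = 0.7392 yr. Assumed inputs are p0 (share at home at start), h (switching hazard per year) and k (death plus transplant hazard per year from day 90), with h and k constant.

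- 1 − KM = p0 + (1 − p0)[1 − exp(−hT)]
- Cumulative incidence = p0 + (1 − p0){1 − exp(−ht) + exp(−ht) · h/(h + k) · [1 − exp(−(h + k)(T − t))]}

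With p0 = 0.05 and h = 0.05:

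- 1 − KM = 0.05 + 0.95 × 0.04809 = 9.57%, whatever the value of k.
- At k = 0.15, cumulative incidence = 0.05 + 0.95 × (0.01224 + 0.98776 × 0.25 × 0.13743) = 9.39%.
- At k = 0.40, cumulative incidence = 0.05 + 0.95 × (0.01224 + 0.98776 × 0.11111 × 0.28298) = 9.11%.

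| k per year | 1 − KM | Cumulative incidence | Excess (points, unrounded inputs) |
|---|---|---|---|
| 0.15 | 9.57% | 9.39% | 0.18 |
| 0.25 | 9.57% | 9.27% | 0.29 |
| 0.40 | 9.57% | 9.11% | 0.45 |

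Over p0 = 0, 0.05, 0.10; h = 0.03, 0.05, 0.10; and k = 0.15, 0.25, 0.40, the excess runs from 0.10 to 0.92 points.

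**Difference hidden between groups with identical KM curves** (p0 = 0.05, h = 0.05). With k = 0.15 against 0.40, a possible panel B contrast, actual uptake differs by 0.27 points. With k = 0.20 against 0.25, a possible seasonal contrast, it differs by 0.06 points.

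**Cross-check among in-center starters only.** Suppose 1 − KM is 10% at day 360. If 10%, 20% or 30% die or are transplanted in days 91 to 360, cumulative incidence is 9.6%, 9.2% or 8.8%, so the curve is about 4%, 8% or 13% too high in relative terms. The last case gives 1.2 points. It lies outside the range above because 30% corresponds to k = −ln(0.70)/0.7392 = 0.48 per year, higher than 0.40.

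**Home starters as a share of events.** For two equal groups A and B, the share is (pA + pB) / [pA + pB + (1 − pA)·CA + (1 − pB)·CB]. Here C is the cumulative incidence above with p0 = 0, using k = 0.15 in A (not hospitalized) and 0.40 in B (hospitalized).

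- Low end: h = 0.10, switching hazard ratio 1.2, home at start 5% and 2%. The share is 0.07/(0.07 + 0.95 × 0.0902 + 0.98 × 0.1006) = 28%.
- High end: h = 0.03, hazard ratio 0.8, home at start 10% and 8%. The share is 0.18/(0.18 + 0.90 × 0.0280 + 0.92 × 0.0210) = 80%.

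**Illustration for Cox B.** These are unadjusted two-group simulations (20 data sets of 200,000 per scenario, Efron ties, reference switching 0.05 per year, k as above), hospitalized against not. Home starters are either dropped or kept as events at day 0.5.

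| True switching HR | Home at start (not / hospitalized) | Dropped | Kept |
|---|---|---|---|
| 1.0 | 5% / 4% | 1.00 | 0.89 |
| 1.0 | 5% / 2% | 0.99 | 0.67 |
| 1.2 | 5% / 4% | 1.20 | 0.98 |
| 0.8 | 5% / 4% | 0.80 | 0.80 |

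For season with equal switching, the kept hazard ratio is 0.93 to 0.97 against 1.00 dropped. At reference switching of 0.10 per year, the third row's kept value is about 1.05, so the direction no longer changes.

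**The case against.** The strongest reply is that the first part concerns only the vertical scale of a descriptive figure. The inferential analyses of time to home dialysis are the log-rank test and Cox B, and censoring competing events is proper for cause-specific hazards. The 90-day rule removes competing events from the first quarter of follow-up, and the seasonal distortion, which is what the title "Seasonal Differences in Home Dialysis Uptake and Initiating Dialysis in the Hospital" puts first, is negligible. All of this stands and limits the size of the point. It does not make one minus Kaplan-Meier the proportion taking up home dialysis, and readers will take a figure on uptake that way. That mortality differs between the panel B groups is an assumption; the SAP gives no rate.

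On home starters, a reader might infer that the SAP leaves two estimands equally open. It does not. The unrestricted any-use indicator in 3) b, applied to the whole cohort, points to counting them as events. Only the entry time is missing. The home-at-start logit also reports start modality separately, though it does not say how those patients enter Cox B.

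A reader might also take the simulated hazard ratios as the expected shift in Cox B, or conclude that its direction is in doubt. The planned model adjusts for access type at start, prior nephrologist care, comorbidities and facility factors. Access type is plausibly tied to start modality, and the simulations include none of these covariates. Reversal appears only under some inputs.

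**Conclusion.** The point holds as a modest estimator error in Figure 2 plus a missing entry rule. With constant hazards and the assumed ranges, the curves overstate uptake at day 360 by about 0.1 to 0.9 percentage points. The overstatement is unequal in panel B if mortality differs by hospitalization, and of no practical consequence between seasons. The documents do not support a claim that the log-rank test or Cox B is invalid, or that the seasonal comparison is materially biased.

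The entry rule matters because home starters are about 28% to 80% of events for switching of 0.03 to 0.10 per year, so dropping them by default would change what Cox B measures. By how much the planned adjusted hazard ratio would move cannot be judged from the SAP. Outcome 3) a also plans "Indicator for whether patient is alive by end of month 3, 6, 9, 12"; that indicator serves the month-specific outcomes and does not address the competing events in Figure 2.

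**What to change.** - **Figure 2:** plot Aalen-Johansen cumulative incidence from the first date of dialysis, with death and transplant as competing events and home starters counted as uptake at day 0.
- **Log-rank test and Cox B:** keep both and label them cause-specific.
- **Entry rule:** in line with 3) b, keep home starters in Cox B as events at a stated small positive time. State the same rule for the log-rank test, and say that the hazard ratio combines starting at home with later switching.
- **Optional addition:** a Cox model restricted to in-center starters, labelled as a switching analysis and read beside the home-at-start logit. It conditions on start modality, itself an outcome of the same exposures, and it gives up the home-starter events.

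The cost is a different curve estimator on the same data and a few SAP sentences. No new data are needed.

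### The robust standard errors name no cluster level: hospitalization effects look too precise if facilities differ, and season effects too if season-by-year variation remains

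*SAP*

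**What the plan says.** Under Planned Analyses, Regressions, the SAP specifies "Robust standard errors for all models". No cluster variable is named there or elsewhere.

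- **Exposures.** The logits and the Cox model share one exposure line: "Exposure: season of year, whether hospitalized (and type of hospitalization)".
- **Outcomes.** The logits cover "Outcome: home dialysis at start, months 3, 6, 9, 12", each as its own regression. The Cox model covers time to home dialysis.
- **Season.** Cohort construction, item 2: "Create season/year variables based on the first date of dialysis", with four levels ("Season is winter, spring, summer, fall").
- **Accrual.** Cohort construction, item 1: "Identify incident adults who started dialysis from 12/1/2007 – 11/30/2017".
- **Calendar time.** Covariates, 4d: "Yearly level fixed effects (an indicator for each year as defined above)". There is no season-by-year term.
- **Facilities.** Covariates, 4b, "Facility characteristics": profit status, chain, size, staffing ratio and ESRD Network. There is no facility effect.

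**The concern.** A sandwich variance without clusters corrects for unequal variances but still treats patients as independent given the covariates. The plan has two groupings where that may fail, and each bears on a different exposure.

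**Facility.** Facilities may differ in how often they use home dialysis and in how many of their patients start in hospital, beyond what five measured characteristics explain. Hospitalization is then partly a between-facility comparison, and its standard error should reflect the number of facilities as well as the number of patients.

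**Season-year.** Season is fixed by start date, so it never varies within one season of one year. Year indicators remove what a whole year shares. They do not remove what is particular to one winter or one summer. Whatever remains is shared by every patient in that cell, and the season contrast rests on 10 winters against 10 summers.

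At stake are confidence intervals and p-values for both named exposures. The only sensitivity analysis planned, complete cases, cannot reveal either problem.

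**Working it through.** The SAP gives no sample size, home-use rate, intracluster correlation (ICC) or power figure, so there is no figure of its own to reproduce. Everything below except the cell count rests on stated assumptions.

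**1. Number of cells.** December 2007 to November 2017 is 10 December-to-November years. 10 × 4 seasons = 40 cells, 10 per season.

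**2. Hospitalization and facility.** Design effect = 1 + (m − 1) × ICCx × ICCy, where m is patients per facility, x is hospital start and y is home use. Assume 9% home use and 50% hospital starts. Integrating over normal facility effects on the log-odds scale, SDs of 0.35 and 0.6 for hospital start give ICCx = 0.029 and 0.077. SDs of 1.0 and 1.5 for home use give ICCy = 0.086 and 0.180.

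| SD x | SD y | m = 50: design effect, SE factor | m = 100: design effect, SE factor |
|---|---|---|---|
| 0.35 | 1.0 | 1.12, 1.06 | 1.25, 1.12 |
| 0.35 | 1.5 | 1.26, 1.12 | 1.52, 1.23 |
| 0.6 | 1.0 | 1.32, 1.15 | 1.66, 1.29 |
| 0.6 | 1.5 | 1.68, 1.30 | 2.37, 1.54 |

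Example, last cell: 1 + 99 × 0.077 × 0.180 = 2.37, and √2.37 = 1.54. Coverage of a nominal 95% interval is 2Φ(1.96/factor) − 1, which falls from about 94% at 1.06 to about 80% at 1.54.

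Simulated null logits, 150 runs each, agree in pattern:
- SDs 0.35 and 1.0, m = 50: no understatement.
- SDs 0.6 and 1.0, m = 50: mean SE 0.043 against a true SD of 0.048 (ratio 1.12), coverage 91%.
- SDs 0.6 and 1.5, m = 50: 0.038 against 0.052 (1.37), coverage 84%.
- SDs 0.6 and 1.5, m = 100: 0.035 against 0.057 (1.63), coverage 74%. An SD from 150 runs carries a relative error of about 1/√(2 × 149) = 6%, so 1.63 is compatible with the formula's 1.54.

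Facility-clustered intervals covered 95% in the last two settings.

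**3. Season and facility.** Null simulations used facility SDs of 1.0 to 1.5 log-odds, patients of each facility starting in all seasons, and no season-year shock. Unclustered and facility-clustered standard errors for winter were 0.0629 and 0.0629, 0.0566 and 0.0565, and 0.0281 and 0.0282. Facility sharing leaves season essentially untouched.

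**4. Season and season-year.** Design effect = 1 + (m − 1)ρ, with ρ = SD²/(0.09 × 0.91), where SD is the between-cell spread left after adjustment and m is patients per cell. SD = 0.25 points gives ρ = 0.0025²/0.0819 = 7.6 × 10⁻⁵; SD = 0.5 points gives 3.1 × 10⁻⁴.

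| Patients per cell | SE factor, SD 0.25 points | SE factor, SD 0.5 points |
|---|---|---|
| 2,500 | 1.09 | 1.33 |
| 6,250 | 1.22 | 1.71 |
| 10,000 | 1.33 | 2.01 |

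The true size of a nominal 5% test is 2(1 − Φ(1.96/factor)): about 7% at 1.09 and 33% at 2.01. On the log-odds scale these SDs are 0.0025/0.0819 = 0.03 and 0.005/0.0819 = 0.06. With an SD of 0.01 log-odds or less, the factor is at most 1.04 for up to 400,000 patients; with zero it is 1.00.

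A simulation with 100,000 patients and season and year indicators gave a true SD of 0.0326 against a mean unclustered SE of 0.0281 at a shock SD of 0.05 log-odds (coverage 91%), and 0.0453 against 0.0282 at 0.10 (coverage 79%).

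**5. Would an ordinary 40-cluster sandwich do?** A cell-level simulation with 13 parameters (intercept, 3 seasons, 9 years) gave an SE about 0.82 of the true SD. Coverage was 87.7% with z limits, 88.7% with t on 39 df and 89.2% with t on 27 df. A bias-reduced (CR2) sandwich with t limits covered about 94%.

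**The case against.** The case against has five parts.

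- **The word robust may have meant cluster-robust.** That is possible. A reader might infer that the plan declares patients independent; it does not say so. But even on the kind reading no cluster unit is fixed, and the choice changes the hospitalization intervals.
- **Shared facilities might be thought to narrow the season intervals.** They do not, as step 3 shows: season varies within each facility. That stronger reading is dropped.
- **The season-year variance is assumed.** This stands. The factor of 2.0 needs the largest assumed SD and the largest cells together. The models also contain hospitalization type, so a severe respiratory winter would act partly through a term already there. What matters is the variation left after that, and nobody can read it from the SAP. It is therefore unsupported to say outright that the season intervals are too narrow.
- **The target may be descriptive.** If the aim is only to describe starts in 2007 to 2017, realised differences between winters belong to the quantity described. The SAP does not say which target it means. This is a good reason to make the season-year analysis a sensitivity analysis.
- **Remedies can misfire.** This stands too. Step 5 shows that an ordinary 40-cluster sandwich can do worse than no clustering when shocks are small. Clustering season terms one way and hospitalization terms another leaves no single covariance matrix for the sums of main effects and interactions in analysis C.

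**Conclusion.** The point holds in two parts of unequal firmness.

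Firmer: no cluster level is named, and hospitalization standard errors are too small whenever hospital starts and home use both vary between facilities after adjustment. The factor is about 1.0 to 1.5 for the assumed facility SDs and sizes, with coverage from about 94% down to about 80%.

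Conditional: season standard errors are too small if season-by-year variation survives adjustment. The factor is 1.1 to 2.0 under the stated assumptions and close to 1 if that variation is near zero.

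A reader might infer that the season results are already invalid; the document gives no variance that would show it. Changing the text is worthwhile all the same, because both exposures are named in every regression.

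**What to change.** Replace the sentence on robust standard errors with: 'Standard errors clustered on dialysis facility for all models.'

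Add to the planned sensitivity analyses: 'Season coefficients re-estimated allowing for dependence within the 40 season-year cells.' Name one method that is valid with so few clusters:
- a bias-reduced (CR2) sandwich with a t reference;
- a wild cluster bootstrap;
- a season-year random effect; or
- a regression of the 40 cell-level estimates on season and year, with t on 40 − 13 = 27 df.

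An ordinary 40-cluster sandwich with z or t limits alone should not be used. Use one covariance matrix per model, so that the sums in analysis C have a defined variance.

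Cost: facility clustering is one sentence and one variance option. The sensitivity analysis takes a little more work, since it has to be carried through the 10 imputations and Rubin's rules. Intervals will be somewhat wider.

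### Hospital start is a title question with no valid seasonal test or model, and the adjusted season effects on home dialysis are conditional on hospitalization, with no adjusted total effect beside them

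*SAP*

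**What the plan says.** Under Outcomes, item 3c of the SAP is "Whether the patient had a hospitalization in the 14 days prior to first_se (include if first_se occurs during the hospitalization", then classified by type. The planned analyses use it as follows.

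- **Table 2:** "Descriptive statistics (frequencies and percentages) of each hospitalization type by season of year. Compute the ratio in frequency between winter and summer". No test or interval is named.
- **Figure 1:** panel A is "Y axis: # of in-center patients, X axis: time" and panel B is the same for home patients. Both have one series for patients who start with a hospitalization and one for those who start without. Item C reads "C) Compute log rank test (p-value)".
- **Figure 2:** Kaplan-Meier curves of time to home dialysis, panel A by season and panel B by hospitalization, with "C) Compute log rank test (p-value) for A & B".
- **Regressions A and B:** the outcomes are home dialysis at start and at months 3, 6, 9 and 12 (logit) and time to home dialysis (Cox). Both carry the line "Exposure: season of year, whether hospitalized (and type of hospitalization)".
- **Regressions C:** "Repeat A and B but interact the exposures", followed by combinations that give the season effect within hospitalization status and the reverse.
- **Sensitivity analysis D:** complete cases only.

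The covariates for all models include, at 4.a.vii, "Type of dialysis access at the start of dialysis".

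**The concern.** There are two linked problems.

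First, hospital start is half of the title and a listed outcome, but no model has it on the left-hand side. The one test that might seem to cover it, under Figure 1, does not fit the figure.

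Second, season and hospitalization enter the home dialysis models together. If winter brings more hospital starts, and patients who start in the hospital are less likely to use home dialysis, hospitalization lies on the path from season to home dialysis. Holding it fixed removes that part of the seasonal difference. Access type at the start of dialysis can lie on the same path, so taking out hospitalization alone would not restore the total effect.

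At stake is the reading of the results. The adjusted models could show no seasonal difference although one exists and runs through the other half of the title. If the Figure 2A curves and the regressions disagree, nothing planned would show whether the covariates or the conditioning on hospitalization caused it.

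**Working it through.** The SAP states no rate, effect size or sample size on this point, so there is no figure to reproduce. The check has a tally from the text and then an illustration on assumed rates.

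**Step 1. Tally of planned analyses**

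| Question | Planned | Valid test? | Adjusted? |
|---|---|---|---|
| Hospital start by season | Table 2 | none named | no |
| Hospital start by season | Figure 1, log-rank | no | no |
| Time to home dialysis by season, total | Figure 2A, log-rank | yes | no |
| Home dialysis at start and months 3, 6, 9, 12 by season, total | none | no | no |
| Home dialysis by season, given hospitalization | A, B, C | yes | yes |

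The Figure 1 test fails for two reasons. A log-rank test needs a time origin, an event and a risk set for each patient; Figure 1 has counts on a calendar axis. And its groups are hospitalized versus not, so even if it could be run it would not compare seasons. Figures 2 and 3, by contrast, specify Kaplan-Meier curves with censoring.

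**Step 2. Total versus conditional odds ratio**

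All inputs are assumptions:
- hospital start: 40% in summer, h = 44% or 48% in winter;
- home dialysis in summer: p0 = 12% or 15% if not hospitalized, p1 = 3% or 5% if hospitalized;
- direct season OR, within hospitalization status: 1.00, 0.95 or 0.90.

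Formulas:
- P(summer) = 0.60 × p0 + 0.40 × p1
- P(winter) = (1 − h) × p0′ + h × p1′, where p0′ and p1′ have their odds multiplied by the direct OR
- total OR = odds(P winter) / odds(P summer)
- share left out = 1 − log(direct OR) / log(total OR)

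Largest gap with direct OR 1.00 (h = 0.48, p0 = 0.15, p1 = 0.03):
- P(summer) = 0.60 × 0.15 + 0.40 × 0.03 = 0.1020
- P(winter) = 0.52 × 0.15 + 0.48 × 0.03 = 0.0924
- total OR = (0.0924/0.9076) / (0.1020/0.8980) = 0.896

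Smallest gap (h = 0.44, p0 = 0.12, p1 = 0.05):
- P(summer) = 0.0920, P(winter) = 0.0892, total OR = 0.967

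Over all 8 combinations:

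| Direct (conditional) OR | Total OR | Share of total log OR left out |
|---|---|---|
| 1.00 | 0.896-0.967 | all |
| 0.95 | 0.853-0.919 | 39-68% |
| 0.90 | 0.810-0.871 | 24-50% |

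Non-collapsibility of the odds ratio does not drive this. With hospital start held at 40% in both seasons, p0 = 0.15, p1 = 0.03 and direct OR 0.95, p0′ = 0.1436 and p1′ = 0.0285. Then P(winter) = 0.60 × 0.1436 + 0.40 × 0.0285 = 0.0976, and the total OR is 0.952.

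A second set of assumed rates gives smaller gaps at one end: hospital start 50% in summer and 52-60% in winter, home start 4-8% if hospitalized and 10-14% if not, no direct effect. The total OR is then 0.879-0.995 against a conditional 1.00.

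**Step 3. Dropping hospitalization but keeping access type**

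Assumed: catheter share 85% or 95% if hospitalized and 60% or 70% if not; logit(home) = −1 + bH × hospitalized + bC × catheter, with bH = −0.5 or −1.0 and bC = −1.0 or −2.0; hospital start as in Step 2; season acting only through hospitalization. A population logit of home dialysis on season and access type gives a season OR of 0.935-0.989, against a total OR of 0.892-0.975. Access type alone removes 17-77% of the total log OR.

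**Step 4. The Table 2 ratio**

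If the percentage hospitalized, p, is the same in both seasons, a ratio of counts is (p × N winter) / (p × N summer) = N winter / N summer. With 0-10% more starts in winter (assumed), the ratio is 1.00-1.10 with no seasonal difference in the risk of a hospital start.

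**The case against.** The strongest reply is that the conditioning is deliberate. The SAP gives hospitalization the same standing as season, and Regressions C ask for season effects within hospitalization status. That is a legitimate target and should stay. It does not supply the total seasonal difference, which the title also asks for.

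A second reply is that the SAP never says outright that the two exposures enter one model. That is true, and separate models are a possible reading. But A says only that outcomes are run separately, and the instruction in C to interact the exposures makes sense only if both are already in A and B. If separate models are meant, the SAP should say so, and access type would still be in them.

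Third, Figure 2A already tests the total difference, and confounding may be slight. The cohort runs from 12/1/2007 to 11/30/2017, ten whole winter-to-fall years under the SAP's December rule, so calendar year has little room to confound season, and Table 1 will show covariate balance by season. This stands in part: the adjusted and unadjusted totals may turn out close. But Figure 2A covers only time to home dialysis, not the five logit outcomes.

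Fourth, Table 2 does report hospital start by season, a reader could derive a crude test from it, and frequency may mean a percentage. All fair; the adjusted estimate is still missing, and the ratio needs only a clarifying word and an interval.

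Finally, the sizes are all assumed, and the shares left out take a direct effect in the same direction as the indirect one. That is a real limit on the figures. An opposing direct effect does not remove the problem, though. With direct OR 1/0.95 = 1.05, h = 0.48, p0 = 0.15 and p1 = 0.03, p0′ = 0.1567 and p1′ = 0.0315. Then P(winter) = 0.52 × 0.1567 + 0.48 × 0.0315 = 0.0966 and the total OR is 0.94, so the conditional and total effects would point in opposite directions.

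**Conclusion.** The concern holds and should be fixed. Two parts rest on the text alone: hospital start, a title question and listed outcome, has no model and no valid seasonal test, and the log-rank test under Figure 1 is wrong for that figure. The third part rests on the natural reading that A and B hold both exposures: their season coefficients are then conditional on hospitalization and on access type at start, and the total difference is tested only without adjustment and only for time to home dialysis.

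How far the conditional and total effects differ in this cohort is unknown. The ranges above show that it could be enough to turn a total odds ratio near 0.90 into a reported 1.00, and also that it could be negligible (0.995 against 1.00). The planned models remain valid for the narrower question they answer.

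**What to change.** 1. **Figure 1:** replace the log-rank test with a test of season on the proportion starting with a hospitalization: a chi-square test, or the model in item 2.
2. **New model for outcome 3c:** a binary logit of hospitalization, or a multinomial logit of its type, on season, with year effects and baseline covariates that the hospitalization cannot have changed. Leave out access type at start.
3. **Regressions A and B:** fit them first with season and that same covariate set, without hospitalization or access type, as the total adjusted seasonal difference. Keep the present models as a second step, labelled as conditional on hospitalization.
4. **Table 2:** take the winter/summer ratio on percentages, with a 95% confidence interval.

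The SAP should write out the covariate list for items 2 and 3. Access type clearly goes. The authors also need to decide on the CMS 2728 comorbidities and the facility characteristics, because the SAP does not say whether they are recorded before or after a hospital start.

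The cost is SAP wording and a few extra model runs on data already in the planned cohort. The downside is one more set of estimates to report.
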